2.7.2 Duration of follow-up

Summary information regarding the follow-up of subjects in the FAS will be displayed by arm in order to describe the maturity of data and quality of follow-up.

Randomization period, duration between randomization and cut-off date, and follow-up times for DFS/OS are defined as follows:

- Randomization (recruitment) period = (Date of last subject randomized - Date of first subject randomized + 1)/30.4375 (months).
- Duration between randomization date and data cut-off date = (Data cut-off date – Date of randomization + 1)/30.4375 (months).
- Follow-up time elapsed from study start reference date= (Date of event or censoring – randomization date + 1)/30.4375 (months) regardless of censoring. Date of event or censoring is the same as the one defined for the primary analyses.

The follow-up time for DFS/OS derived from KM method will also be summarized.

2.7.3 New primary cancer other than lung cancer

Summary statistics will be tabulated for subjects with new primary cancer other than lung cancer based on "Diagnosis and extent of new primary Cancer Other than Lung" eCRF page. This analysis will include the following: number of subjects with new primary cancer, primary site of cancer, the time from randomization to initial diagnosis, predominant histology/cytology, staging system and metastatic sites.

2.8 Safety analyses

All safety analyses will be based on the safety set.

2.8.1 Adverse events (AEs)

AE summaries will include all AEs occurring during on-treatment period. All AEs collected in the AE (e)CRF page will be listed along with the information collected on those AEs e.g. AE relationship to study treatment, AE outcome, etc. AEs with start date outside of on-treatment period will be flagged in the listings.

AEs will be summarized by number and percentage of subjects by primary system organ class (SOC), preferred term (PT), and treatment. A subject with multiple occurrences of an AE will be counted only once in the respective AE category. A subject with multiple CTCAE grades for the same preferred term will be summarized under the maximum grade. AE with missing CTCAE grade will be included in the 'All grades' column of the summary tables.

In AE summaries, the primary system organ class will be presented alphabetically and the PTs will be sorted within primary SOC in descending frequency. The sort order for the PTs will be based on their frequency in the investigational treatment.

The following AE summaries will be produced by treatment; overview of AEs and deaths, AEs by SOC and PT, summarized by relationship, seriousness, leading to treatment discontinuation, leading to dose interruption, requiring additional therapy, and leading to fatal outcome. In addition, a summary of serious adverse events with number of occurrences will be produced (an occurrence is defined as > 1 day between start and prior end date of record of same PT).

2.8.1.1 Adverse events of special interest / grouping of AEs

Data analysis of AESIs

An AE of special interest (AESI) is a grouping of AEs that are of scientific and medical concern specific to canakinumab. These groupings are defined using MedDRA terms, SMQs (standardized MedDRA queries), HGLTs (high level group terms), HLT (high level terms) and PTs. Customized SMQs (Novartis MedDRA queries, NMQ) may also be used. A NMQ is a customized group of search terms which defines a medical concept for which there is no official SMQ available or the available SMQ does not completely fit the need. It may include a combination of single terms and/or an existing SMQ, narrow or broad. The groups are defined according to the MedDRA terms defined in the program Case Retrieval Strategy (CRS) document and will be summarized. The latest version of the CRS document available at the time of the analyses will be used. For each specified AESI, number and percentage of subjects with at least one event of the AESI occurring during on treatment period will be summarized.

Summaries of these AESIs will be provided by treatment (specifying grade, SAE, relationship, leading to treatment discontinuation, leading to dose interruption, hospitalization, death, etc.).

A listing of all grouping levels down to the MedDRA PTs used to define each AESI will be generated.

Table 2-6 provides current AESI groupings. CRS at the time of database lock will govern how these groups will be summarized:

Table 2-6 AESI groupings

AESI grouping
Infections
Opportunistic infections
Opportunistic infections (based on SMQ Broad)

Opportunistic infections (based on SMQ Narrow)

Neutropenia

Abnormal liver parameters

Thrombocytopenia

Immunogenicity/allergenicity

Autoimmunity reactions

Malignancy

Interactions with vaccines

Pulmonary complications: pulmonary hypertension and interstitial lung disease

Injection site reactions

Time to onset of AESI

Time to onset of CTC grade ≥ 2 AESI is defined as the time from the start of treatment to the start date of the first incidence of an event of CTC grade ≥ 2 , i.e., time in days is calculated as (start date of first occurrence of the event) – (date of first dose of study treatment) +1.

In the absence of an event during the on-treatment period, the censoring date applied will be the earliest of the following dates:

- End date of on-treatment period (end of study treatment + 130 days).
- death date
- Start date of new antineoplastic therapy before experiencing any CTC grade ≥ 2 AESI.
- Data cut-off date.
- withdrawal of informed consent date

Time to onset of CTC grade ≥ 2 AESI will be summarized using the Kaplan-Meier method by AESI grouping and treatment. Median time to onset and its 95% CI will be provided and ascending Kaplan-Meier plots will be generated by treatment. The analysis of time to onset of AESI will be performed *only* for AESI groupings of infections, opportunistic infections, neutropenia, DILI (Hepatic transaminase and bilirubin elevations) and thrombocytopenia (if there are sufficient number of events).

The same analysis will be repeated for time to onset of CTC grade ≥ 3 AESI with similar censoring rules applied.

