7.1.4 Discontinuation of study treatment

Subjects who discontinue study treatment should NOT automatically be considered withdrawn from the study. See Table 7-1 for the required assessments of these subjects after discontinuation of study treatment. Subjects who discontinue study treatment during the treatment phase should be scheduled for a visit within 7 days or as soon as possible after the last dose of study treatment, at which time all of the assessments listed for the EOT visit will be performed. If a subject withdraws from treatment at a study visit, EOT assessments that are already part of that scheduled study visit do not need to be repeated. The disposition page should be completed, giving the date and reason for stopping treatment.

For subjects who discontinue treatment for reasons other than documented disease recurrence, initiation of new antineoplastic therapies, death, lost to follow-up, or withdrawal of consent, assessments must continue to be performed according to Table 7-1 until disease recurrence, withdrawal of consent by the subject, subject is lost to follow up, death or the sponsor terminates the study for up to five years.

Confidential

Subjects may voluntarily discontinue from the study for any reason at any time. If a subject decides to discontinue from the study, the investigator should make a reasonable effort (e.g. telephone, e-mail, letter) to understand the primary reason for this decision and record this information in the subject's chart and on the appropriate eCRF pages. They may be considered withdrawn if they state an intention to withdraw, fail to return for visits, or become lost to follow-up for any other reason. The investigator must also contact the IRT to register the subject's discontinuation from study treatment.

At a minimum, all subjects who discontinue study treatment, including those who refuse to return for a final visit, will be contacted for safety evaluations during the 130 days following the EOT visit (see Section 7.1.6.1).

The investigator may discontinue study treatment for a given subject if, he/she believes that continuation would be detrimental to the subject's well-being.

In addition to mandatory study drug discontinuation criteria listed in Table 6-2, treatment must also be discontinued under the following circumstances:

- Pregnancy
- Study Terminated by Sponsor
- Subject/guardian decision
- Physician decision

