- Non-compliance, as defined by missing any single dose greater than 42 days from the intended day of the next scheduled dose.
- Initiation of a new antineoplastic therapy

Subjects who become pregnant during the trial must be withdrawn (Section 8.4). Subjects who become pregnant must cease all tumor assessments regardless of whether or not they developed recurrence.

The appropriate personnel from the site and Novartis will assess whether study treatment should be discontinued for any subject whose treatment code has been broken inadvertently for any reason.

Discontinuation from study is when the subject permanently stops receiving the study treatment, and further protocol-required assessments or follow-up, for any reason.

If the subject agrees, a final evaluation at the time of the subject's study discontinuation should be made as detailed in the assessment table (refer to Table 7-1).

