7.1.6 Follow up evaluations

7.1.6.1 Safety follow up

All subjects will be followed for AEs and SAEs for at least 130 days following the EOT visit. Subjects will present to the clinical site every 28 days, for a total of five follow-up visits (see Table 7-1). At the end of this period, the investigator should assess and discuss with the subject any AEs observed and concomitant medications taken since discontinuation of study treatment. Subjects whose treatment is permanently discontinued due to an AE (clinical or based on abnormal laboratory value) must be followed until resolution or stabilization of the event, whichever comes first. In case of an abnormal laboratory value, blood tests should be repeated until resolution or stabilization.

If a new antineoplastic therapy is initiated after discontinuation of study treatment, only SAEs suspected to be related to study treatment will be collected in the Adverse Events eCRF.

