7.1.7 Lost to follow-up

For subjects whose status is unclear because they fail to appear for study visits, or fail to respond to any site attempts to contact them, without stating an intention to discontinue from study treatment or discontinue from study or withdraw consent (or exercise other subject's data privacy rights), the investigator should show "due diligence" by documenting in the source documents steps taken to contact the subject, e.g. dates of telephone calls, registered letters, etc. A subject should not be considered lost to follow-up until due diligence has been completed. Subjects lost to follow up should be recorded as such on the appropriate disposition eCRF.

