8.1 Adverse events

8.1.1 Definitions and reporting

An adverse event is defined as the appearance of (or worsening of any pre-existing) undesirable sign(s), symptom(s), or medical condition(s) that occur after a subject's signed informed consent has been obtained.

Abnormal laboratory values or test results occurring after informed consent constitute adverse events only if they induce clinical signs or symptoms, are considered clinically significant, require therapy (e.g., hematologic abnormality that requires transfusion or hematological stem cell support), or require changes in study medication(s).

Adverse events that begin or worsen after informed consent should be recorded in the AE eCRF. Conditions that were already present at the time of informed consent should be recorded in the medical history eCRF. Adverse event monitoring should be continued for at least 130 days following the EOT visit. Adverse events (including lab abnormalities that constitute AEs) should be described using a diagnosis whenever possible, rather than individual underlying signs and symptoms. When a clear diagnosis cannot be identified, each sign or symptom should be reported as a separate Adverse Event.

If a new antineoplastic therapy is initiated after discontinuation of study treatment, only SAEs suspected to be related to study treatment will be collected in the Adverse Events eCRF.

Confidential

Adverse events will be assessed and graded according to the Common Terminology Criteria for Adverse Events (CTCAE) version 5.0.

If CTCAE grading does not exist for an adverse event, the severity of mild, moderate, severe, and life-threatening, death related to the AE corresponding respectively to Grades 1 - 5, will be used. Information about any deaths (related to an adverse event or not) will also be collected though a death form.

The occurrence of adverse events should be sought by non-directive questioning of the subject during the screening process after signing informed consent and at each visit during the study. Adverse events also may be detected when they are volunteered by the subject during the screening process or between visits, or through physical examination, laboratory test, or other assessments. As far as possible, each adverse event should be evaluated to determine:

- The severity grade (CTCAE v5.0 Grades 1-5)
- Its duration (Start and end dates)
- Its relationship to the study treatment. Reasonable possibility that AE is related:

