“Note: EOT will be included if EOT is performed within 7 days of permanent discontinuation of study treatment”

Safety follow-up phase

Safety follow-up 1	26 days after treatment discontinuation	[EOT visit date+8; EOT date +39]
Safety follow-up 2	52 days after treatment discontinuation	[EOT visit date+40; EOT date +65]
Safety follow-up 3	78 days after treatment discontinuation	[EOT visit date+66; EOT date +91]
Safety follow-up 4	104 days after treatment discontinuation	[EOT visit date+92; EOT date +117]
Safety follow-up 5	130 days after treatment discontinuation	[EOT visit date+118; EOT date +143]

Post treatment efficacy follow-up phase

Post treatment follow-up (Efficacy follow up)	Every 26 weeks in Year 2 and 3; Every 52 weeks in Year 4 and 5	First time window: [upper bound of the last previous time windows with assessment + 1; TA date + TA interval at next visit/2] Otherwise : [TA date - TA interval at this visit/2; TA date+TA interval at next visit/2]
7 days post disease progression (PRO only)	Within 7 days post disease progression	[disease progression date+1; disease progression date +21]
28 days post disease progression (PRO only)	28 days post disease progression	[disease progression date+22; disease progression date +42]

[a] Study Day 1 = randomization date and PRO assessment on Cycle 1 Day1 will be baseline for PRO if randomization date is not Cycle 1 Day1.

Last contact date

The last contact date will be derived for subjects not known to have died at the analysis cut-off using the last complete date among the following (Table 2-2):

Table 2-1 Last contact date data sources

Source data	Conditions
Date of Randomization	No condition

Source data	Conditions
Last contact date/last date subject was known to be alive from Survival Follow-up page	Subject status is reported to be alive, lost to follow-up or unknown.
Start/End dates from further antineoplastic therapy	Non-missing medication/procedure term.
Start/End dates from drug administration record	Non-missing dose. Doses of 0 are allowed.
Date of disease recurrence	No condition
Laboratory/PK collection dates	Sample collection marked as 'done'.
Vital signs date	At least one non-missing parameter value
Performance Status date	Non-missing performance status
Start/End dates of AE	Non-missing verbatim term

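### The time-to-onset analysis of AESIs has no censoring bound at the last AE assessment, so up to 130 days without routine ascertainment count as event-free; the effect is small and mainly concerns infections

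*SAP*

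**What the plan says.** SAP 2.8.1.1 plans Kaplan-Meier curves of time to first grade ≥2 AESI, repeated for grade ≥3 with similar censoring. They cover infections, opportunistic infections, neutropenia, liver events and, if events suffice, thrombocytopenia. The censoring rule reads: "In the absence of an event during the on-treatment period, the censoring date applied will be the earliest of the following dates". The list opens with the end of the on-treatment period (end of study treatment plus 130 days) and closes with "withdrawal of informed consent date"; between them stand death, new antineoplastic therapy and data cut-off. SAP 2.1.1 defines end of study treatment as the last non-zero dose, so the window does not shorten for a subject who disappears.

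The protocol keeps the two groups at issue apart from consent withdrawal:

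- Section 7.1.4: "Discontinuation from study is when the subject permanently stops receiving the study treatment, and further protocol-required assessments or follow-up, for any reason".
- Section 7.1.7, on loss to follow-up: "A subject should not be considered lost to follow-up until due diligence has been completed".
- Section 7.1.5 reserves consent withdrawal for subjects who no longer wish to take part and also refuse further collection of personal data.

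SAP 2.5.3 likewise lists consent withdrawal and loss to follow-up as separate DFS censoring reasons.

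On ascertainment, protocol 8.1.1 has AEs sought "after signing informed consent and at each visit during the study". Section 7.1.6.1 states: "All subjects will be followed for AEs and SAEs for at least 130 days following the EOT visit". Section 7.1.4 adds that all subjects who stop treatment, "including those who refuse to return for a final visit, will be contacted for safety evaluations during the 130 days following the EOT visit".

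**The concern.** Kaplan-Meier assumes that a subject in the risk set would be seen to have the event if it occurred. Once someone is unreachable or has ended all follow-up, that is no longer reliably so. Keeping the subject at risk adds denominator time with almost no chance of a numerator event, which lowers the curve in each arm.

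Infection is the main known risk of canakinumab (protocol 1.3.1.2.1). Infections and opportunistic infections have no other planned time-to-onset analysis. Neutropenia, thrombocytopenia and liver tests share the gap in their AESI curves, but SAP 2.8.3 gives each a laboratory-based onset analysis bounded by the last on-treatment sample. If loss differed by arm, the gap could also produce a false difference between the curves.

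**Working it through.** **Window.** The SAP describes 130 days as about five terminal half-lives. The protocol gives a half-life of 26 days, and 5 × 26 = 130, so the figure reproduces. A subject lost straight after a dose carries the full 130 days.

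**Inputs.** From the documents: 18 doses 21 days apart (last dose at 17 × 21 = 357 days), 28-day safety visits, 130-day window (end at 357 + 130 = day 487, or 1.333 years). The documents give no loss rate for AE collection. The 3% yearly OS loss (protocol 10.9) and 5% yearly DFS dropout (protocol 10.8, cause undefined) serve as proxies. AESI hazards of 0.15 and 0.40 per year are assumed. Safety visits are placed at +28, +56, +84, +112 and +130 days, and observation ends at the last visit before loss.

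**Subjects lost before day 487.** 1 − 0.97^1.333 = 4.0%; 1 − 0.95^1.333 = 6.6%.

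**Unobserved days per lost event-free subject.** Losses up to day 385 carry 130 days; losses in the later intervals carry 102, 74, 46 and 18. Unweighted: (385×130 + 28×102 + 28×74 + 28×46 + 18×18)/487 ≈ 116. Weighting by loss and event-free probability gives about 118-119.

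**Extra time at risk.** Roughly 0.03 × 119/365 = 1.0% and 0.05 × 119/365 = 1.6%; numerical integration gives 1.0% and 1.7%.

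**Shift in the curve.** True risk is 1 − exp(−0.15 × 1.333) = 18.1% and 1 − exp(−0.40 × 1.333) = 41.3%. The shift is approximately survival × cumulative hazard × extra-time fraction. For 3% loss and hazard 0.15: 0.819 × 0.200 × 0.0098 = 0.16 points. Numerical integration gives:

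| Yearly loss | Hazard/yr | True risk, day 487 | SAP rule | Understatement (points) | If safety contact reaches half |
|---|---|---|---|---|---|
| 3% | 0.15 | 18.1% | 17.96% | 0.16 | 0.08 |
| 3% | 0.40 | 41.3% | 41.0% | 0.32 | 0.16 |
| 5% | 0.15 | 18.1% | 17.85% | 0.27 | 0.14 |
| 5% | 0.40 | 41.3% | 40.8% | 0.54 | 0.27 |

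**Against sampling error.** With 1382 randomized (protocol Amendment 03), an assumed even split of 691 per arm and full follow-up to day 487, the standard error is √(0.181 × 0.819/691) = 1.5 points and √(0.413 × 0.587/691) = 1.9 points. The largest shift is 0.54/1.9 ≈ 0.3 standard errors.

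**Between arms.** With equal loss and a true hazard ratio of 1.3, the difference moves from 4.77 to 4.70-4.73 points (base hazard 0.15) and from 8.67 to 8.60-8.63 (0.40). With equal hazards and loss of 3% versus 5%, a spurious 0.1-0.2 points appears, in either direction.

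**Median.** It is reached by day 487 only if the hazard is at least ln 2/1.333 = 0.52 per year, so neither assumed hazard reaches it. At 0.6 per year it moves from day 422 to day 426 (3% loss) or 430 (5%).

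**Heavier loss.** A separate simulation, with 20% yearly treatment stop and hazards up to 1.0 per year, gave understatement at day 378 of at most 0.7 points at 5% loss, about 1.4 at 10% and about 3 at 20%.

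**The case against.** The best defence is that last dose plus 130 days matches the planned AE collection window. Protocol Table 7-1 shows AE collection as continuous to 130 days after EOT. AEs may be volunteered between visits (8.1.1), SAEs in the window are reportable when the site learns of them (8.2.2), and safety contact is planned even for subjects who refuse a final visit. This stands in part. A reader might infer that no AE can be recorded after loss, and the documents do not support that: routine ascertainment stops, but late-learned events can still arrive. Planned contact also shrinks the affected group, chiefly to unreachable subjects and those who end all follow-up. It does not reach those subjects, and the rule still counts their time as event-free.

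One might also take the bounds in SAP 2.8.3 (last sample) and SAP 2.4.1 (exposure cut at last contact before loss) as proof of internal contradiction. That goes too far. A laboratory onset can be seen only at a sample, and the exposure rule concerns dosing. They show only that stopping at the last observation is familiar practice in this SAP.

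Protocol 7.1.4 says that subjects who fail to return or are lost may be considered withdrawn. This does not bring them under the consent bound, because 7.1.5 defines consent withdrawal more narrowly.

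The size objection is fair: the effect is well inside sampling error.

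**Conclusion.** The rule is wrong as written, because it counts time without routine ascertainment as event-free, but the consequence is minor. Under the assumed loss and hazards, onset risk at day 487 is understated by about 0.1-0.5 points, at most about 0.3 of a per-arm standard error. The loss rates are borrowed from efficacy planning and the hazards are not in the documents. The model also has no deaths, new therapy, consent withdrawal or early treatment stop, although the separate simulation with early stopping gives a similar size at 5% loss.

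A reader might infer that infection risk is materially hidden or that the arm comparison is distorted. The documents do not support either reading. The curves are descriptive, the AESI n (%) tables do not use this censoring, the shift is nearly equal in both arms unless loss differs, and the close-out SAP lists no time-to-onset output. Nor can the trough-quartile onset curves in SAP 2.10.1.4 be called affected outright: that section states no censoring rule, so the point applies only if they share the rule in 2.8.1.1. This is an inexpensive correction worth making, and no safety conclusion would be expected to turn on it.

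**What to change.** Add one item to the list in SAP 2.8.1.1, for both the grade ≥2 and grade ≥3 analyses: the date of the last visit or documented safety contact at which AEs were assessed, for subjects lost to follow-up or who discontinued the study, whether or not later known to have died. In the main curve, count only events with onset on or before that date and list later-reported events separately. Otherwise late-learned events would count while event-free lost subjects were censored earlier, which biases the curve upward. Use the same rule for the 2.10.1.4 curves if they share this censoring.

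Derive the date from recorded visits and any recorded safety contacts. Do not reuse the OS date in SAP 2.1.1: "The last contact date will be derived for subjects not known to have died at the analysis cut-off", and it draws on survival-page and antineoplastic-therapy dates that can fall after AE collection stopped.

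The cost is a short SAP edit and one small new derivation. Visit dates exist; whether telephone contacts at which AEs were assessed are recorded in a usable field is not shown in the documents and should be checked first. If they are not, visit dates alone would serve.

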6.1.5 Treatment duration

Subjects will be treated with canakinumab or placebo for 18 cycles (approximately 54 weeks) or until they experience any of the following: first NSCLC recurrence as determined by the investigator, unacceptable toxicity that precludes further treatment, treatment discontinuation at the discretion of the Investigator or subject, or start of a new antineoplastic therapy, or death, or lost to follow-up, whichever occurs first.

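### Ascending Kaplan-Meier curves for time to first grade 2+ and 3+ AESI censor death and new antineoplastic therapy, so they are an upper bound on the proportion of subjects who have the AESI before those events

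*SAP*

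**What the plan says.** SAP 2.8.1.1 plans a Kaplan-Meier analysis of time from first dose to the first grade 2+ AESI. It covers infections, opportunistic infections, neutropenia, liver events and thrombocytopenia, and the list closes with a condition that there be enough events. On display it says: "Median time to onset and its 95% CI will be provided and ascending Kaplan-Meier plots will be generated by treatment".

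A subject without the event is censored at the earliest of five dates: last dose plus 130 days, death, data cut-off, consent withdrawal, or "Start date of new antineoplastic therapy before experiencing any CTC grade ≥ 2 AESI". For higher grades: "The same analysis will be repeated for time to onset of CTC grade ≥ 3 AESI with similar censoring rules applied". SAP 2.10.1.4 plans the same curves by quartile of average trough concentration.

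No cumulative incidence estimate is planned for this analysis. The same SAP section does plan crude counts: "number and percentage of subjects with at least one event of the AESI occurring during on treatment period will be summarized".

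Protocol 8.1.1 limits safety collection once a subject who has stopped study drug starts a new antineoplastic therapy: "only SAEs suspected to be related to study treatment will be collected in the Adverse Events eCRF". Protocol 7.1.6.1 and 8.2.2 repeat this.

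**The concern.** Kaplan-Meier treats a censored subject as still able to have the event, at the same rate as those who remain under observation. For a subject who has died this cannot be true. For a subject who has started new therapy, full AE collection has ended, and most such subjects will have recurrent cancer, so assuming an unchanged AESI rate is not neutral. An ascending curve is naturally read as the percentage of subjects who have had the AESI by a given month. With these events censored it answers a different question: what the risk would be if neither death nor new therapy occurred. The SAP does not say that this is the target.

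Infection is the main risk that the protocol names for the drug (1.3.1.2.1), and it is the group most likely to be common enough for the difference to show.

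**Working it through.** **Design figures first.** The documents give no figure for the AESI analysis. The design inputs that supply the competing hazard do reproduce.
- Power: sqrt(392/4) × |ln 0.716| − 1.960 = 1.347, which is 91.1%. Allowing for the futility bound (Z = 0.226) and the final bound (Z = 1.969) gives 90.45%, against 90.4% in Protocol 10.8.
- Expected DFS events at 42 months, with 50 subjects a month for 30 months and 5% yearly dropout: 395, against 392.

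**Inputs from the documents**
- Placebo median DFS is 48 months (Protocol 10.8). Hazard h = ln 2/48 = 0.01444 per month, so 1 − exp(−12h) = 15.9% have a DFS event by month 12.
- With the design hazard ratio of 0.716, the canakinumab hazard is 0.01034 per month, or 11.7% by month 12.
- Length of the risk window: the 18th dose falls 17 × 21 = 357 days after the first, and 357 + 130 = 487 days = 16.0 months.

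**Assumptions**
- AESI risk: 20-40% for a common AESI, with 10% and 2-5% shown for contrast. Neither document gives a grade 2+ or 3+ rate for this trial.
- f is the share of the DFS hazard that becomes death or new therapy inside the window, from 0.5 to 1. Neither document gives a new-therapy rate.
- Deaths before any new therapy: 1-3% per year.
- All hazards constant.

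**Formulas.** With AESI risk p at month t:
- AESI hazard: λ = −ln(1 − p)/t. Competing hazard: μ = f × h.
- 1 − KM = 1 − exp(−λt) = p.
- Cumulative incidence = λ/(λ + μ) × [1 − exp(−(λ + μ)t)].

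**Worked case:** p = 30%, t = 12, f = 1, placebo. λ = 0.02972 and λ/(λ + μ) = 0.6730. The bracket is 0.4114, so cumulative incidence is 27.7%. The overstatement is 30.0 − 27.7 = 2.3 points.

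**Overstatement at 12 months, death and new therapy both competing (percentage points)**

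| AESI risk at 12 months | Placebo, f = 0.5 | Placebo, f = 1 | Canakinumab, f = 1 |
|---|---|---|---|
| 2% | 0.1 | 0.2 | 0.1 |
| 5% | 0.2 | 0.4 | 0.3 |
| 10% | 0.4 | 0.8 | 0.6 |
| 20% | 0.8 | 1.6 | 1.2 |
| 30% | 1.2 | 2.3 | 1.7 |
| 40% | 1.5 | 3.0 | 2.2 |

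**At 16 months**, with p the risk at 16 months and f = 1, placebo: 0.2 point at 2%, 0.5 at 5%, 2.1 at 20%, 3.0 at 30% and 3.9 at 40%. A simulation of the SAP censoring rules, with new therapy starting 1-2 months after recurrence, gave somewhat less at 16 months: 1.2-1.8 points at 20%, 1.7-2.7 at 30% and 2.2-3.5 at 40%, over both arms.

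**Death alone competing**, μ = 1-3% per year. At 12 months: 0.05-0.15 point for p = 10% and 0.18-0.54 for p = 40%. At 16 months: 0.07-0.19 and 0.24-0.72. Overall about 0.05-0.7 point.

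**Between arms** at 30% risk, f = 1, design hazard ratio true: 2.31 − 1.68 = 0.6 point at 12 months and 3.03 − 2.21 = 0.8 point at 16 months. With 1382/2 = 691 subjects per arm, the standard error of one arm's 12-month curve is about 1.8 points, so that of a difference is about 1.8 × sqrt(2) = 2.6 points. The differential is about a quarter of it.

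**The case against.** The strongest objection is that new therapy does not prevent an infection. What stops is full recording of AEs, and loss of observation is an ordinary reason to censor, if possibly an informative one. Censoring there targets AESI risk unaffected by other anticancer drugs, which may themselves cause neutropenia, infection or liver events. That is a legitimate safety question, and the objection stands: new therapy as a competing event is a choice of estimand. Nearly all of the 1-3 points depends on that choice; only death strictly rules out a later event.

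It is also said that the crude counts already report the risk. They are unaffected by the Kaplan-Meier problem, but they do not replace a time-to-event estimate. The final DFS analysis requires only 3 months' minimum follow-up (Protocol 10.8, SAP 3.1) against a window of about 16 months, so late-randomized subjects may be only partly observed and crude percentages may run low.

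Three stronger readings are tempting, and the documents do not support them.
- *The curves are overstated by 1-3 points as a matter of fact.* The AESI and new-therapy rates behind that figure are assumptions.
- *The comparison of arms is materially distorted.* The differential is under 1 point at 30% risk and needs a true DFS effect; the close-out SAP records that the primary endpoint was not met.
- *The curves should match the crude tables.* Aalen-Johansen curves would not match them either, because early discontinuers remain censored 130 days after the last dose.

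The close-out SAP lists no AESI Kaplan-Meier figure. That list is described as a subset of the primary outputs, so it does not show that the curves were dropped.

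**Conclusion.** The point holds as a minor improvement to an unlabelled descriptive display. It is not an error that touches any test or conclusion. The direction is certain: with death and new therapy censored, one minus Kaplan-Meier cannot lie below the cumulative incidence of the AESI before those events.

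The size is conditional. It is about 0.8-3.0 points at 12 months if the AESI risk is 20-40% and half to all of the placebo DFS hazard becomes death or new therapy. Using the DFS hazard as the upper limit is itself an assumption, since SAP 2.5.1 foresees some switching to newly approved therapy before recurrence. Death alone, or AESIs of 2-5%, bring the overstatement below 1 point. The practical relevance is therefore to infections.

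**What to change.** In SAP 2.8.1.1, and for the exposure-quartile curves in 2.10.1.4, plot Aalen-Johansen cumulative incidence by group with death as a competing event. As a stated estimand choice, also show it with start of new antineoplastic therapy as a competing event, giving the reason that full AE collection stops there. Keep last dose plus 130 days, data cut-off and consent withdrawal as censoring. Report cumulative incidence with 95% CI at fixed months, for example 3, 6, 12 and 16; a median is not reached for any AESI whose curve stays below 50%. If the Kaplan-Meier curve is retained, label it as risk in the absence of death and new therapy.

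The cost is a change of SAP wording and a small amount of programming (the EVENTCODE option in SAS PROC LIFETEST), with no new data. The displayed percentages will be slightly lower.
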